## The IMPACT Study: Inflammatory Responses, Mood and Physical Fitness after Cancer Treatment

### OVERVIEW

Inflammation, a robust and reliable predictor of all-cause mortality in older adults, is one of the key candidate mechanisms for age-related decrements in physical function and disability [1, 2]. Chronic inflammation signals a heightened risk for disability and mortality even in the absence of clinical disease [3-5]. Inflammation frequently accompanies tumor growth and can also be amplified by cancer treatments [6].

Inflammation is higher in sedentary than in active individuals [7-11]. Indeed, when cardiorespiratory fitness is assessed objectively by maximal exercise testing, poorer physical fitness ( $VO_2\text{peak}$ ) is associated with higher inflammation [12-15]. In this context it is noteworthy that cancer survivors' average cardiorespiratory fitness is consistently ~30% lower than their *sedentary* age mates without a cancer history [16, 17]. The reduced physical activity and associated deconditioning that frequently occur during cancer and its treatment lead to a decrease in the capacity for physical performance [18, 19]. With deconditioning, normal activities become more fatiguing, resulting in greater fatigue and lessened functional capacity over time [18, 19]; excessive proinflammatory cytokine production is thought to promote this downward spiral [18, 19]. Consistent with this argument, breast cancer survivors with lower levels of physical activity have a higher risk of premature death [20].

An immune challenge provides a useful paradigm for studying an individual's ability to limit inflammatory responses to infection or tissue injury. We will use a typhoid vaccine as a peripheral immune stimulus to assess the magnitude and kinetics of a transient inflammatory response and associated behavioral changes that have particular importance for breast cancer survivors--depressive symptoms, fatigue, cognitive problems, and pain [21-23]. We address a novel question: does poorer cardiorespiratory fitness heighten the magnitude and duration of inflammatory responses to immune challenges, as well as magnifying maladaptive behavioral responses?

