#### **A.5 Innovation and Potential Impact**

Attenuated reactivity to and enhanced recovery from challenge are among the mechanisms researchers have suggested to account for exercise's health benefits [120]. However, the studies addressing the benefits of cardiorespiratory fitness during acute challenge have focused on cardiovascular and cortisol reactivity and recovery from psychological laboratory stressors [120], not immune challenge and inflammatory responsiveness. This project adopts an innovative model to look at reactivity and recovery from a very different perspective: no prior research has addressed whether cardiorespiratory fitness affects people's inflammatory responses to an

immune challenge. Furthermore, in addition to the kinetics of inflammatory reactivity and recovery, the vaccine model will provide original data on changes in mood, fatigue, cognitive problems, and pain and their relationship to cardiorespiratory fitness.

Immune challenges are a frequent occurrence, and the ability to minimize inflammatory responsiveness influences the total burden that infectious challenges or tissue injury place on an individual. Larger, more frequent, or more persistent inflammatory changes have negative consequences for health. If better cardiorespiratory fitness dampens or limits inflammatory responsiveness, then this study could demonstrate a new and novel mechanism through which regular exercise produces its substantial health benefits.

Persistent activation of innate immunity is a key feature of chronic inflammatory disorders. Use of a typhoid vaccine provides a way to safely activate the innate immune response and study subsequent downstream responses; as a consequence, the vaccine bypasses the thorny issues related to reverse causation and confounding that are so common in chronic disease studies. *Differences in acute phase responses will provide insight into the downstream effects on the initiation and progression of both acute and chronic inflammatory diseases as well as the associated behavioral symptomatology [121].*

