Diagnostic, treatment, and staging data will be obtained from medical records. These data will include (but are not limited to): types and dates of diagnostic procedures, histology, cytology, tumor grade, available genetic tests, comorbidities, major medications, and hormonal treatment status. Where possible we will use the James Cancer Registry and Outcomes Management Department and/or the OSU Information Warehouse to provide us with information regarding our participants' treatment.

**Online/phone screening:** To confirm eligibility, we will collect data on cancer stage, time since treatment, and treatment regimen. We will also assess vaccination history, medication use, comorbidities, and physical activity.

**Screening session:** When subjects come for their in-person screening appointment at the Clinical Research Center (CRC), a hospital research unit, nurses will draw blood for assessment of anemia and hemoglobin A1C (to confirm  $< 6.5$ ). The nurses will also assess any potential phlebotomy problems, and measure blood pressure, height, and weight. Women will be interviewed using the mood and anxiety disorder modules from the Structured Clinical Interview for DSM-V [171, 172], nonpatient version.

**Cardiorespiratory fitness:** Peak oxygen consumption ( $VO_2\text{peak}$ ) will be evaluated at a screening visit using a graded cycle ergometry exercise test, starting at 25 watts and increasing by 25 watts every two minutes, with continuous monitoring via 12-lead EKG (MedGraphics Cardio2, Cardio Perfect).  $VO_2\text{peak}$  [173] will be calculated from 10-second averages of breath-by-breath expired air (MedGraphics Cardio2, Breeze Suite). Declines in cardiorespiratory fitness may result directly from chemotherapy's toxic effects on pulmonary, cardiac, hematological, vascular, and skeletal muscle function, as well as deconditioning following treatment [174]. Cardiorespiratory endurance is the gold standard measure of physical fitness; low values predict mortality [175-177]. To avoid influencing vaccine/placebo responses, this session will not occur on the day before a full-day CRC visit.

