## C. Study Design and Procedures

**Study Design:** This study will have a balanced, randomized, double-blind, crossover design. The two ~9.5-hour sessions will be scheduled 10-30 days apart.

**Randomization and masking:** Following completion of the screening appointments, women will be randomly assigned to either the vaccine/placebo or the placebo/vaccine sequence using a treatment sequence prepared and maintained by the Data Manager. The research assistants will not have access to the condition assignments. The CRC nurse who administers the vaccine or placebo will not be the same nurse who will be measuring the vital signs throughout the day and drawing blood. The Data Manager will not be involved in any

other aspects of the research, including data collection or blood sample analyses. Blinding will be assessed for subjects, nurses, and research assistants.

**Standardized activity prior to study days:** Participants will be asked to consume their last meal no later than 7:30 pm the night before each of the day-long CRC admissions. Participants will avoid alcohol use and any strenuous physical activity two days prior to their appointments [168]. Aspirin, nonsteroidal anti-inflammatory drugs, and vitamins will be discontinued at least one week prior to each evaluation.

Anyone with a recent illness will be rescheduled. A temperature greater than 99.7°F on admission will result in cancellation of the current session.

**Clinical Research Center (CRC) visits, overview:** Women will have a small intravenous catheter inserted on admission to the CRC, and baseline samples will be drawn following a 20-30 minute adaptation period. Following the baseline blood draw, and prior to breakfast, women will complete baseline mood questionnaires and brief cognitive tests. Following completion of baseline measures a nurse will inject **saline (the placebo) or Typhoid capsular polysaccharide vaccine (Typhim-Vi, Aventis Pasteur)** into the non-dominant deltoid muscle. Women will receive a standardized breakfast (and, later, lunch).

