The three specific aims for the proposed study are to evaluate (1) the effect of cardiorespiratory fitness on vaccine response, (2) the effect of age and depressive symptoms on vaccine response, and (3) the moderating effect of fitness on the age- and depression-related effects on vaccine response. Since each woman will serve as her own control by receiving both the vaccine and the placebo injection, the corresponding hypotheses all involve complex interactions: (1) the two-way interaction between fitness and injection type (vaccine/placebo), (2) the two-way interaction between age/depression and injection type, and (3) the three-way interaction of fitness by age/depression by injection type. Sample size requirements are considerably higher for testing higher-order interaction terms, thus we based required sample size on the tests of the third specific aim: the three-way interaction between fitness, age/depression, and injection type, while ensuring adequate power for the first two aims as well. Throughout we assumed 2-tailed tests with an 0.05 level of significance and used SAS PROC GLMPOWER for calculations.

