**Data Analysis Plan** Each subject will have two visits (vaccine, placebo), and within each visit the primary outcomes (inflammation, behavioral responses) will be measured before injection and then serially (every 90 minutes) over the subsequent ~7.5 hours. Primary data analyses will use area under the curve (AUC) to summarize within-visit inflammatory and behavioral responses for each outcome. Hierarchical linear regression models (HLMs) will then be used to capture within-subject correlation across the two visits. If significant effects are found, secondary analyses will use more complex multi-level HLMs to model the individual time points within visit in order to identify at what time in the post-injection period effects arise.

For Hypothesis 1, baseline relationships between cardiorespiratory fitness and inflammation and behavioral outcomes will be evaluated using HLMs; subjects will have two baseline measurements, one before each injection, so an HLM is needed to control for the within-subject correlation. Outcomes in these models will be baseline (pre-injection) inflammation, depressive symptoms, cognitive problems, pain, and fatigue, and predictors will include cardiorespiratory fitness and visit (first or second). Tests of the main effect of cardiorespiratory fitness will investigate baseline relationships between these variables. The effect of vaccine on these outcomes over time will also be investigated using HLMs. AUC for each outcome at each visit will be the dependent variable, and predictors will include injection type (vaccine/placebo), cardiorespiratory fitness, and their interaction, as well as the baseline (pre-injection) outcome level. Separate models will be fit for each of the primary outcome AUCs (inflammation, behavioral responses) and the effect of interest will be the two-way interaction of cardiorespiratory fitness by injection type (which is a between-subject\*within-subject interaction). This term will allow us to investigate differences in response for the vaccine compared to placebo (injection type effect) and how these differences differ by fitness level (cardiorespiratory fitness by injection type interaction).

For Hypothesis 2a, baseline relationships between inflammation and age as well as the effect of age on vaccine responses will be investigated using HLMs similar to those described for Hypothesis 1 with age

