replacing cardiorespiratory fitness. For Hypothesis 2b similar HLMs will again be used, with depressive symptoms replacing cardiorespiratory fitness. For Hypothesis 2c, the HLMs with inflammation and behavioral AUC responses as outcomes will be modified by including both age and depression and their interaction as predictors. The test of the age by depression interaction will test whether the combination of older age and high depressive symptoms produces greater responses than the effect of either alone.

HLMs with AUC for inflammatory markers as well as behavioral responses as outcomes will also be used to test Hypothesis 3. Predictors will include injection type (vaccine/placebo), cardiorespiratory fitness, and age or depression, as well as all interactions and the baseline outcome level. Separate models will be used to test moderation of age and depression effects. To test whether cardiorespiratory fitness moderates the effect of age/depression on outcomes we will test the three-way interaction of injection type by age/depression by cardiorespiratory fitness. This is a three-way interaction, and we note that the primary interest is actually in the contrast testing the age/depression by cardiorespiratory fitness interaction for the vaccine injection. The post-placebo information serves to reduce error variance by allowing each woman to serve as her own control.

In all models we will control for BMI and insulin resistance to avoid possible confounding. Additionally, secondary analyses will control for use of aromatase inhibitors or tamoxifen; by including these variables as covariates, we will assess whether these medications impact cardiovascular (i.e., blood pressure, HRV) and inflammatory responses to the vaccine. Separately, we will assess whether tamoxifen or aromatase inhibitor use is related to cardiovascular variables and inflammation at baseline.

In secondary analyses, we will also assess antidepressant use as a possible confounder and control for this in analyses. We note again that the crossover design allows each woman to serve as her own control, thus mitigating the effect of possible confounders.

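### The protection from confounding and reverse causation that the plan claims holds for vaccine versus placebo, but not for the fitness, age and depression interactions that its aims test

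*Combined protocol and SAP*

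**What the plan says.** Section A.5 argues that a vaccine activates innate immunity safely so that downstream responses can be studied, and concludes that "the vaccine bypasses the thorny issues related to reverse causation and confounding that are so common in chronic disease studies". The paragraph before it says that, if better fitness dampens inflammatory responsiveness, "this study could demonstrate a new and novel mechanism through which regular exercise produces its substantial health benefits". The closing paragraph of the Objectives starts from an association between fitness and vaccine response, and goes on to speak of fitness limiting inflammation and constraining symptoms. The Data Analysis Plan adds that "the crossover design allows each woman to serve as her own control, thus mitigating the effect of possible confounders".

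The design is as follows. Under section C, "women will be randomly assigned to either the vaccine/placebo or the placebo/vaccine sequence"; nothing else is randomised. Under section B, VO2peak "will be evaluated at a screening visit using a graded cycle ergometry exercise test". Age and depressive symptoms are likewise observed. Of the three aims, Power and Sample Size says that "the corresponding hypotheses all involve complex interactions". For Hypothesis 1 the Data Analysis Plan says that "the effect of interest will be the two-way interaction of cardiorespiratory fitness by injection type", and describes this as a between-subject by within-subject term.

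The Hypothesis 1 response model contains injection type, fitness, their interaction and the baseline outcome. BMI and insulin resistance are added to all models. Endocrine therapy and antidepressant use are left to secondary analyses. No interaction between an adjustment covariate and injection type is named.

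**The concern.** Randomising the order of injections protects the comparison of vaccine with placebo. It does not protect the comparison of that difference between fit and unfit women, because nobody was assigned to be fit. Self-control removes stable differences in level between women. It leaves in place any difference in response that travels with fitness.

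What is at stake is the reading of the main tests. A significant fitness-by-injection term could be reported as a mechanism of exercise, with the design cited as the reason to set confounding aside. The same term could arise because less fit women are older or more depressed, or because a long-standing inflammatory tendency has lowered their fitness.

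**Working it through.** **1. The plan's own power figure.** The bypass claim rests on no number, so the plan's power basis is reproduced first and then used for the illustration in step 4. Inputs from Power and Sample Size: vaccine means 10, 15.2, 11.2, 25.2; placebo means 8.5, 9.1, 8.7, 9.3; SD 7.7; covariate correlation 0.75; n = 180; two-sided 5%.

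- Three-way contrast: (25.2 − 11.2 − 15.2 + 10) − (9.3 − 8.7 − 9.1 + 8.5) = 8.8.
- Residual SD: 7.7 × √(1 − 0.75²) = 5.09. With 180/8 = 22.5 observations per cell, the contrast variance is 5.09² × 8/22.5 ≈ 9.22.
- Noncentrality: 8.8²/9.22 ≈ 8.40 on 1 and 171 degrees of freedom. Power is 82.2%, against 81% stated.
- Depression by injection: (20.2 − 10.6) − (9.2 − 8.6) = 9.0 points. Fitness by injection: (18.2 − 12.6) − (9.0 − 8.8) = 5.4 points.

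On this basis the two-way powers are over 99.9% for depression and 94% for fitness. The plan states them the other way round. That is a separate slip and does not affect this point.

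**2. What the interaction estimates.** For a woman with both visits, let D be her vaccine response minus her placebo response. A main-effect covariate with the same value at both visits, such as BMI from screening height and weight, cancels out of D. The fitness-by-injection coefficient is then the slope of D on fitness across women. If D also depends on a trait W with coefficient g, leaving out W-by-injection biases that slope by g × (difference in mean W between fitness groups). A main effect of BMI does not remove this. The same is true of insulin resistance, apart from any change in it between visits. Only a covariate-by-injection term does.

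**3. The paths that the plan itself names.**

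- *Confounding.* Hypothesis 1 expects fitter women to have fewer depressive symptoms. Hypothesis 2b expects depression to intensify the vaccine response, and Hypothesis 2a expects age to amplify it. Neither age nor depression is in the Hypothesis 1 model.
- *Common cause.* Section B says chemotherapy toxicity may lower fitness directly.
- *Reverse path.* Of fatigue and deconditioning, the Overview says that "excessive proinflammatory cytokine production is thought to promote this downward spiral".

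**4. Illustration under assumed values.** Assume that fitness has no effect, that the plan's 9.0-point depression-by-injection contrast holds for all women, and that half the women fall in each fitness and each depression group. High depression is commoner by Δ in the low-fitness group; Δ is an assumption, not a document figure. The spurious interaction is 9.0 × Δ. On the plan's basis the noncentrality is (2 × 9.0 × Δ)²/9.22.

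| Δ | Spurious interaction (points) | Noncentrality | p < 0.05, plan's basis | p < 0.05, simulated differences |
|---|---|---|---|---|
| 0.10 | 0.9 | 0.35 | 9% | 11–15% |
| 0.20 | 1.8 | 1.41 | 22% | 34–47% |
| 0.30 | 2.7 | 3.16 | 42% | 65–80% |
| 0.40 | 3.6 | 5.62 | 65% | 88–97% |

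The last column simulates within-woman differences (2,000 runs per setting; residual SDs of 7.7 and 5.8, each times √(1 − 0.75²); within-woman residual correlation 0 to 0.5). Adding depression-by-injection to the simulated model brought the rate back to about 5% in every row.

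**The case against.** The strongest reply is that the sentence in A.5 concerns induced inflammation and its downstream responses, set against chronic disease studies in which inflammation is only observed. For that contrast it is fair, and Hypothesis 1 contains the contrast. This stands. The overreach lies in letting the claim, and the own-control statement in the Data Analysis Plan, cover the trait interactions.

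The plan also does not ignore confounding. It adjusts all models for BMI and insulin resistance, recruits to separate fitness from central adiposity, restricts to two chemotherapy regimens and postmenopausal women, and excludes smokers, diabetes, inflammatory disease and anti-inflammatory drugs. These measures narrow the problem. They do not deal with age or depression in the Hypothesis 1 test, nor with reverse causation. The Hypothesis 3 models do hold fitness and age or depression together with all interactions, but the test of interest there is the three-way term.

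The conclusions are conditional in form. That stands in part: the condition is on the result, not on the causal reading of it.

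A reader might infer that a significant fitness result is as likely under reverse causation as under a true fitness effect. The documents do not support that. VO2peak is measured before the injection, so the acute response cannot cause it; a long-standing tendency must be assumed. The Overview's spiral begins with reduced activity, and does not say that strong reactors become unfit. Reverse causation is impossible for age. Standardised reverse paths of −0.2 to −0.3, with reliability of the difference of 0.4 to 0.8, would give significance in 39% to 96% of trials. Those inputs have no source in the documents, and the result shows only that 180 women suffice to detect correlations of about 0.13 to 0.27, whatever their cause.

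**Conclusion.** The point holds in a limited form. The stated protection is a property of the randomised vaccine-versus-placebo contrast, not of the interactions that the plan names as its effects of interest. Those are observational associations between a measured trait and a within-woman response. Confounding by age, depression or treatment history is at least as serious a threat as reverse causation.

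The documents do not fix the size of the bias. The 9% to 65% range in step 4 is an illustration. It rests on the plan's hypothesised 9.0-point contrast for a single post-injection mood score, dichotomised traits and assumed prevalence differences; the primary analysis uses area under the curve and continuous traits. It shows that the Hypothesis 1 test can reject well above 5% with no fitness effect. It does not show that this will happen in this trial.

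**What to change.** 1. In section A.5, limit the bypass claim to vaccine versus placebo. State that trait-by-injection results are observational associations open to confounding and, for fitness and depression, reverse causation. Drop the inference to a mechanism of regular exercise. In the closing paragraph of the Objectives, describe fitness as associated with the outcomes.
2. In the Data Analysis Plan, limit the own-control statement to the injection effect and to stable differences in level between women.
3. In the Hypothesis 1 fitness model, add age together with age-, BMI- and insulin-resistance-by-injection terms. Add depression and depression-by-injection as a sensitivity analysis, because depression may lie on the path from fitness to response and adjusting for it could remove part of a real effect.

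Rerunning the models on reported physical activity and requiring agreement with VO2peak would not help. Reverse causation or a shared confounder would move both measures together.

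The cost is wording, four extra coefficients in the main model (the age main effect and three interactions), two more in the sensitivity model, and a more modest conclusion. No new data are needed.
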